4.3.1 Baseline Measurement

DriveID will measure participants' cellphone use while the cellphone is in the car in which the DriveID device is installed. DriveID will also record GPS data. This data will not be accessed in real time by the study team and will only be viewed after the completion of the drive. The participants will not have access to the usage data during the baseline period and will have no interaction with the device as the monitoring occurs.

Coded data on primary and secondary endpoints will be automatically uploaded daily whenever the phone has a Wi-Fi or cellular data connection to the Cellcontrol server and then exported through an encrypted, secure internet connection to Penn's Way to Health IT Platform for management and analysis via linkage of a study ID.

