5.3 Cellcontrol Data

Cellcontrol requires users to enter in basic information to set up the account policy. This includes:

- Username
 - Password
 - Name
 - Phone number
-

- Email

The Cellcontrol app currently tabulates the following data which are uploaded securely to the Cellcontrol server:

- Phone talk time while driving
- Phone usage time while driving (non-talk time phone unlocked and being used for apps, texts, email, etc).
- Phone unlocks while driving
- Speed the car is traveling when the phone is unlocked
- Incidence of hard decelerations converted to a “driving score” and hard accelerations converted to an “eco score”
- Number of incoming calls and texts that are blocked
- GPS, accelerometer, and timestamp data

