6.3.2 Efficacy Analysis

The primary analysis will be based on an intention to treat approach and will include all subjects randomized at the beginning of the intervention period.

The primary efficacy endpoint will be the difference in frequency of cellphone unlocks per hour of driving between weeks 5 and 8 compared with baseline period weeks 2 to 4. The statistical analysis will use relative change models adjusted for age, sex, state, and presence of in-vehicle navigation and phone connectivity systems will compare % change in unlocks per hour with 95% confidence intervals in each intervention arm relative to control arm.

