9 STUDY ADMINISTRATION

9.1 Treatment Assignment Methods

9.1.1 Randomization

Participants will be randomized to one of the four condition groups.. A statistician who is not involved with enrolling subjects will be responsible for creating the randomization chart. We will do block randomization for 8 assignments at a time. Each block will contain the four arm assignments repeated once in a random order. We will create a string that is 250 assignments long. As participants reach the intervention phase they will be assigned to the next available assignment in this string. Once an assignment has been used it is no longer available to be used. Study staff and participants will not be blinded to the condition. Individuals conducting data analyses will use data which blinds them to which group participants are in.

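### The primary efficacy model does not list the baseline unlock rate as a covariate, and it leaves relative change undefined, including for a teen with no baseline unlocks

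*Combined protocol and SAP*

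**What the plan says.** Section 6.1 names unlocks per hour of driving as the primary endpoint. Section 6.3.2 takes the difference "between weeks 5 and 8 compared with baseline period weeks 2 to 4". The analysis "will use relative change models adjusted for age, sex, state, and presence of in-vehicle navigation and phone connectivity systems" and "will compare % change in unlocks per hour with 95% confidence intervals in each intervention arm relative to control arm". It follows intention to treat and "will include all subjects randomized at the beginning of the intervention period".

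The baseline value is available. Section 5.3 lists "Phone unlocks while driving" among the tabulated data, and section 4.3.1, on the baseline period, says "Coded data on primary and secondary endpoints will be automatically uploaded daily". It also precedes allocation, since section 9.1.1 says "As participants reach the intervention phase they will be assigned to the next available assignment in this string".

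No section gives the model's outcome, link, distribution or formula for percentage change. None gives a rule for a teen with zero baseline unlocks or no recorded driving.

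**The concern.** There are two issues, and each depends on what the undefined model turns out to be.

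First, a change score subtracts the whole baseline value, including its week-to-week noise. Using baseline as a covariate lets the data decide how much of it to remove. The covariate list omits the pre-assignment variable most likely to predict the outcome, so a change-score analysis would give wider arm-versus-control intervals than necessary.

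Second, a percentage change computed for each teen divides by that teen's baseline rate. A zero baseline has no percentage change, so the teen would drop out of an analysis meant to include everyone randomized. A ratio with a noisy denominator also averages above zero when nothing has changed, so each arm's reported mean change would mislead.

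The stakes are modest but real. Section 6 says the pilot's data will be used to size future trials, and an inflated variance would carry into that calculation.

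**Working it through.** The plan gives no power, standard deviation, unlock rate or trip length, so it has no figure to reproduce. The documents supply these inputs: up to 250 participants (3.3.2), so 250/4 = 62.5, about 62 per arm; at least five per group (3.2); four trips a week on average (3.4.1), so 4 x 3 = 12 trips in weeks 2-4. Every rate, trip length and variance below is an assumption.

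**Precision, closed form.** With equal SDs s and baseline-to-follow-up correlation r, a change score has variance 2s²(1-r) and a baseline-adjusted outcome has s²(1-r²). The ratio is 2/(1+r).

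| r | variance ratio | CI wider by |
|---|---|---|
| 0.3 | 2/1.3 = 1.54 | 24% |
| 0.5 | 2/1.5 = 1.33 | 15% |
| 0.7 | 2/1.7 = 1.18 | 8% |
| 0.9 | 2/1.9 = 1.05 | 3% |

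**Precision, simulated on the log scale.** This is the natural scale for a percentage change. Assumptions: teen rates gamma with shape 1 and mean 1-10 unlocks/h; trips of 15 minutes, averaging 4.5 h of driving in weeks 2-4 and 6 h in weeks 5-8; independent period effects with log-SD 0.3-0.5; outcome log((unlocks+0.5)/hours). Change-score intervals compared with baseline-adjusted ones were:
- about 62 per arm: 2-10% wider;
- 15 per arm: 1-9% wider;
- 5 per arm: from 3% narrower to 3% wider, so no gain.

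If the log-SD is 0.8, the log-scale variance ratio is 1.19-1.28. Square roots of 1.09 and 1.13 mean intervals 9-13% wider.

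**Zero baseline, only if the change is computed per teen.** The share with no unlocks is (1+mh/k)^(-k) for mean m unlocks/h, h hours and gamma shape k. Twelve trips of 15 minutes give h = 3. With k = 1 the share is 1/4 = 25%, 1/7 = 14%, 1/16 = 6% and 1/31 = 3% at m = 1, 2, 5 and 10. At h = 4.5 it is 18%, 10%, 4% and 2%; there, k = 0.5 gives 32% down to 10%, and k = 2 gives 9.5% down to 0.2%. With no variation between teens (Poisson) and h = 4, it is exp(-4) = 1.8% at 1/h and essentially nil at 5/h. The range is too wide to support any single figure.

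**The three analyses compared.** Two arms of 62, 4 h of baseline and 5.33 h of intervention driving, log-SD 0.5, 2,000 runs per setting. Rejection rates are for a true 30% reduction.

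| mean rate, shape | undefined | per-teen % change | log change | log, baseline-adjusted | control mean % change, no true effect |
|---|---|---|---|---|---|
| 1/h, 1 | 23% | 30% | 36% | 41% | +29% |
| 5/h, 1 | 6% | 43% | 57% | 62% | +40% |
| 10/h, 2 | 0.4% | 52% | 70% | 78% | +38% |

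With no effect, all three rejected in 4-6% of runs. The last column is a ratio artefact: with log-SD 0.5, the mean ratio of two independent period effects is exp(0.5²) = 1.28, or +28%, before any counting noise.

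**The case against.** The strongest reply is that the text does not establish how baseline enters the model. A longitudinal log-link model that takes both periods as outcomes and constrains baseline means to be equal across arms uses baseline about as efficiently as a covariate does. It is also defined at a zero count. The adjustment list might name only the additional covariates. This stands. What can be said is that baseline is not listed and the model is not defined; if such a model is meant, the plan need only say so.

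A reader might infer that the analysis ignores baseline. It does not, because the endpoint is itself a comparison with weeks 2-4. Nor do the documents say that the percentage change is computed per teen, so the zero-baseline problem cannot be asserted outright. The entry rule of recent self-reported texting while driving makes zeros less likely, though it does not exclude them.

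It is also fair that no precision target is missed: this is a feasibility pilot (2.1, 6), and the gain vanishes at five per arm. The 24% figure in the closed form needs a correlation of 0.3, whereas simulated log rates had correlations of 0.64-0.90.

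**Conclusion.** The point holds as a cheap, minor improvement. The baseline unlock rate is recorded before assignment but not listed as a covariate, and the model is too loosely described to tell what that costs. If it is a change score, the cost is intervals about 2-10% wider at about 62 per arm and 1-9% wider at 15 per arm, under the assumed rates and log-SD 0.3-0.5. At five per arm there is nothing to gain.

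If it is a per-teen percentage change, zero-baseline teens are lost and each arm's mean change is inflated upward (+29% to +40% in the simulated control arm with no true change). The number of teens lost cannot be determined from the documents.

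A reader might go on to infer a biased or invalid arm comparison. That is not supported: excluding teens on a value fixed before assignment does not favour an arm, simulated type I error stayed at 4-6%, and section 9.1.1 says "Individuals conducting data analyses will use data which blinds them to which group participants are in". No stated figure is invalidated.

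**What to change.** In section 6.3.2, define the model. Take the weeks 5-8 unlock rate on the log scale as outcome, with arm, the covariates already listed, and the weeks 2-4 unlock rate as a further covariate in a form defined at zero, such as log((unlocks+0.5)/hours). Report 100*(ratio-1) for each blocking arm against control with a 95% CI. A linear model with log((unlocks+0.5)/hours) as outcome is enough.

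A log-link count model with a driving-hours offset is an acceptable alternative at larger sizes. It should not be the default near the floor: in one simulation at five per arm, a negative binomial model with HC3-type standard errors gave intervals 46-65% wider than a plain log-change model.

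Report by arm the teens with no recorded driving in either period. The 0.5 constant solves zero unlocks but not zero hours, so state in advance how those teens are handled.

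The cost is wording only, with no new data. The 0.5 is a convention that must be fixed beforehand, one degree of freedom is used, and precision does not improve at five per arm.

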7 STUDY INTERVENTION

7.1 Description

The study intervention will involve four different conditions to which participants may be randomized: 1 control group and 3 blocking groups.

7.1.1 Education Only (Control) Group

Participants in the control group will complete the Baseline driving period, but at the end of Week 4, instead of DriveID flipping into a blocking mode, the device will remain at baseline settings. It will continue to collect information regarding cellphone use while driving in the background. There will be no observable changes to cellphone functions.

7.1.2 Opt-in Group

The blocking settings for opt-in group participants will require participants to “opt in” to using the blocking features. Blocking settings will be pre-set to block all incoming calls and text messages while the vehicle is in motion, but participants will have to initiate the blocking when they begin driving by activating the device via the phone app. Participants have the ability to override the blocking function while the vehicle is in motion. Number of unlocks can be monitored through logging in to the DriveID website.

7.1.3 Opt-out Group

The blocking settings for opt-out group participants will turn on by default while driving. Blocking settings will be pre-set to block all incoming calls and text messages while the vehicle is in motion, but participants will have the ability to override the blocking. Number of unlocks can be monitored through logging in to the DriveID website.

7.1.4 Opt-out Blocking with parental notification Group

The blocking setting for the opt-out blocking with parental notification group participants will turn on by default while driving. The restrictions will be pre-set to block all incoming calls and text messages while the vehicle is in motion. Parents/guardians will receive a notification every time the teen overrides the block at non-zero speeds. Parents/guardians will have the option to also block outgoing calls as well as all other cellphone functions (i.e. applications). Number of unlocks can also be monitored through logging in to the DriveID website.

8 SAFETY MANAGEMENT

8.1 Adverse Event Reporting

Since the study procedures are not greater than minimal risk, SAEs are not expected. If any unanticipated problems related to research involving risks to subjects or others happen during the course of this study (including SAEs) they will be reported to the IRB in accordance with CHOP IRB SOP 408: Unanticipated Problems Involving Risks to Subjects. AEs that are not serious but that are notable and could involve risks to subjects will be summarized in narrative or other format and submitted to the IRB at the time of continuing review.

Enrolled participants will be provided with contact information of a study team member for reporting of any adverse events that occur during data collection. They will be told to contact regarding any occurrence they feel is an adverse event, including but not limited to, moving violations/citations while participating, traffic accidents, DriveID malfunction, etc.

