1.3 Findings from Non-Clinical and Clinical Studies

The largest, most rigorous study of the crash risk associated with distraction from cellphone use was published in the *New England Journal of Medicine* in January 2014. The authors conducted two studies on the relationship between the performance of secondary tasks, including cell-phone use, and the risk of crashes and near-crashes. To facilitate objective assessment, accelerometers, cameras, global positioning systems, and other sensors were installed in the vehicles of 42 newly licensed drivers (16.3 to 17.0 years of age) and 109 adults with more driving experience.

During the study periods, 167 crashes and near-crashes among novice drivers and 518 crashes and near-crashes among experienced drivers were identified. The risk of a crash or near-crash among novice drivers increased significantly if they were dialing a cell phone (odds ratio, 8.32; 95% confidence interval [CI], 2.83 to 24.42), reaching for a cell phone (odds ratio, 7.05; 95% CI, 2.64 to 18.83), sending or receiving text messages (odds ratio, 3.87; 95% CI, 1.62 to 9.25), reaching for an object other than a cell phone (odds ratio, 8.00; 95% CI, 3.67 to 17.50), looking at a roadside object (odds ratio, 3.90; 95% CI, 1.72 to 8.81), or eating (odds ratio, 2.99; 95% CI, 1.30 to 6.91). Among experienced drivers, dialing a cell phone was associated with a significantly increased risk of a crash or near-crash (odds ratio, 2.49; 95% CI, 1.38 to 4.54); the risk associated with texting or accessing the Internet was not assessed in this population. The prevalence of high-risk attention to secondary tasks increased over time among novice drivers but not among experienced drivers.

The authors concluded that the risk of a crash or near-crash among novice drivers increased with the performance of many secondary tasks, including texting and dialing cell phones. The study was funded by the Eunice Kennedy Shriver National Institute of Child Health and Human Development and the National Highway Traffic Safety Administration.

There is one previous field study using Cellcontrol's cellphone blocking/filtering technology to reduce cellphone use while driving, which was funded by the National Highway and Traffic Safety Administration (NHTSA Contract DOT HS 811 863) and carried out by investigators at the University of Michigan. The abstract of the full report published online in December 2013 states:

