5.4 Post-Baseline Survey

We will collect self-report information on each subject’s driving behaviors for the past thirty days in which they were driving in the baseline period. Information includes how often they report driving and self-report cell phone use.

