5.5 Teen End of Study Survey

We will survey participants via the Way To Health platform. The survey will be constructed in Qualtrics, an online survey tool used by Way To Health, to elicit feedback on the cellphone locking technology. Teen subjects will be asked to report:

- Their feedback on using the cellphone blocking technology
- Feedback on settings/configurations of the cellphone blocking technology
- Perceptions of whether their safety had improved with the use of the technology
- Suggestions for improving the technology and the research study
- Suggestions for future interventions to promote engaged driving

A member of the study team may contact participants over the phone to elaborate upon responses to the end of study survey questions.

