9.7 Payment to Subjects/Families

9.7.1 Payment for time and inconvenience (i.e. compensation)

Participants will be compensated for their time, effort, and inconvenience over the duration of the study:

- Completion of the intake survey
 - Successful installation of DriveID
 - End of Baseline Period (including completion of survey)
 - End of Intervention Period(including completion of survey)
-

- End of Follow up Period(including completion of survey)
- End of Drive Survey Teen Interview

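### Crashes and moving violations are captured only if a teen volunteers them; the surveys already sent to every teen could ask directly

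*Combined protocol and SAP*

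**What the plan says.** Section 8.1 describes passive collection. "Enrolled participants will be provided with contact information of a study team member for reporting of any adverse events that occur during data collection". The instruction that follows is "They will be told to contact regarding any occurrence they feel is an adverse event", and the examples given are "moving violations/citations while participating, traffic accidents, DriveID malfunction, etc". Adverse events that are notable but not serious "will be summarized in narrative or other format and submitted to the IRB at the time of continuing review".

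Participants and staff know the assigned condition (Sections 3.2 and 9.1.1). Section 9.4.1 adds weekly team meetings, which discuss the safety issues that have been observed.

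Teens are surveyed on a schedule:

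- The post-baseline survey (Section 5.4) covers the preceding thirty days: "Information includes how often they report driving and self-report cell phone use".
- The payment list in Section 9.7.1 implies a survey at the end of the intervention, "End of Intervention Period(including completion of survey", but no section describes its content.
- The end-of-study survey (Section 5.5) also goes to teens who withdraw (Sections 3.1.4 and 4.3.4). It asks for feedback on the technology, suggestions, and "Perceptions of whether their safety had improved with the use of the technology".

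Neither these lists, nor those for the intake survey (Section 5.2) and the optional interview (Section 5.6), include a question on crashes or citations.

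**The concern.** The plan names the events it wants to hear about and then waits for them to be volunteered. The teens are 16 or 17, live with a parent, and were enrolled because they admit to texting while driving (Section 3.4.1). All parents may look up phone use in weeks 5 to 10 (Section 4.3.2). It is a fair inference, though not one the documents quantify, that some crashes and tickets would go unreported through forgetting, inertia or reluctance.

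What is at stake is the safety description. Section 5.7 says that no related serious events are expected and that dismissing the block is no more dangerous than an ordinary unlock. If few reports arrive, the reader cannot tell whether few events happened or few were passed on.

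**Working it through.** **Step 1: trace every described capture route.**

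| Event | Unprompted contact | Automatic alert | Listed survey or interview item |
|---|---|---|---|
| Crash | Yes (8.1) | None described; hard decelerations, accelerometer and GPS are logged (5.3) but not linked to crash detection | None listed |
| Moving violation | Yes (8.1) | None | None listed |
| Device problem | Yes (8.1) | Installation error prompts contact from the team (4.2); tampering, app deletion or disabled Bluetooth emails the team in any condition (1.2) | General feedback at study end (5.5) |

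For crashes and citations there is one route. For device problems there are several, but the alerts cover installation and participant actions, and neither is described as detecting a fault during a later drive.

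**Step 2: illustrate the effect on a count.** The documents give no event rate, reporting rate or safety power, so there is no plan figure to reproduce. The inputs are:

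- Enrolment of up to 250 (Section 3.3.2): 250 / 4 = 62.5, taken as 62 per arm, or 4 × 62 = 248 in all.
- A minimum of 5 per arm (Section 3.2).
- Assumed: risk of at least one event per teen of 1% to 10%, and a reported share of 50% to 90%.

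Expected reports = teens × risk × reported share.

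- Risk 1%, all reported: 248 × 0.01 × 1.0 = 2.48.
- Risk 2%, half reported: 248 × 0.02 × 0.5 = 2.48.
- Risk 5%: 248 × 0.05 = 12.4 true events; with half reported, 6.2 are missed.

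The count alone cannot separate the first two cases.

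**Step 3: what zero reports would mean.** With zero reports among n teens, the one-sided 95% upper limit for (risk × reported share) is 1 − 0.05^(1/n). Dividing by the reported share gives the limit for the risk itself.

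- n = 62: 4.7% with full reporting; 4.72 / 0.9 = 5.2% at 90%; 4.72 / 0.5 = 9.4% at 50%.
- n = 5: 45% with full reporting; 45.07 / 0.5 = 90% at 50%.

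Under passive reporting the reported share is unknown, so no limit can be stated.

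**Step 4: could arms be compared if every event were captured?** At the assumed risks, expected events per arm are 62 × 0.01 = 0.6 to 62 × 0.10 = 6.2. Power to detect a halving of risk (two-sided 0.05, normal approximation), shown for 5% against 2.5%:

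- Pooled standard error = √(2 × 0.0375 × 0.9625 / 62) = 0.0341.
- Unpooled standard error = √((0.05 × 0.95 + 0.025 × 0.975) / 62) = 0.0340.
- Power = Φ[(0.025 − 1.96 × 0.0341) / 0.0340] = Φ(−1.23) = 11%.

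The same formula gives 7% for 2% against 1%, and 18% for 10% against 5%. For 80% power the three cases need about 2,319 (2% against 1%), 906 (5% against 2.5%) and 435 (10% against 5%) per arm.

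**The case against.** The strongest defence is that this is a minimal-risk pilot in which spontaneous reporting, backed by weekly team review, is proportionate. Section 8.1 also tells teens by name that crashes, citations and malfunctions count, so the list is not left wholly to what a teen feels. The survey instruments are not in the documents, so an unlisted item may exist. A survey question goes to the same unblinded teen, who may still conceal. All of this stands. It limits the point without answering it: nothing described prompts the teen, and the remedy is nearly free.

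Four stronger readings are tempting, and the documents do not support them:

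- *All three event types rest on volunteering alone.* This is not so for device problems (Sections 1.2, 4.2 and 5.5).
- *Differential reporting will distort a safety comparison between arms.* If control teens reported 80% of events and blocking-arm teens 50%, the apparent risk ratio under no effect would be 0.50 / 0.80 = 0.625, and reversed it would be 1.60. But the direction and size are unknown, Sections 6.2 and 6.3.2 plan no such comparison, and Step 4 shows it would be uninformative anyway. Likewise, no section plans to hand a crash rate to a future trial.
- *A crash count can be projected from Section 1.3.* The cited study found "167 crashes and near-crashes among novice drivers" in 42 novice drivers, but its duration and crash share are not given, and the figure includes near-crashes found with in-vehicle instruments. Only 4 of this trial's 10 weeks are randomized exposure.
- *A serious crash judged unrelated escapes ethics-board reporting.* That depends on an institutional procedure cited in Section 8.1 that is not in the documents.

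**Conclusion.** The point holds for crashes and moving violations: the one described route is unprompted contact from a teen who knows the arm, and no listed survey or interview content asks. Under-counting is likely, and a low count would be uninterpretable. For device problems the gap is narrower and concerns faults during driving.

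The size cannot be estimated from the documents. Under the assumed 1% to 10% risk, about 2.5 to 25 teens of 248 would have an event (248 × 0.01 and 248 × 0.10), and at 50% reporting half of these events would be missed. At smaller enrolment the numbers shrink in proportion. The consequence is a weaker safety description. The primary endpoint, which is measured by the device, is untouched. This is a cheap improvement and rests on the survey content being as listed.

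**What to change.** Add the same three yes/no items, each with a date, to the post-baseline, end-of-intervention and end-of-study/withdrawal surveys in every arm: any crash as driver, any moving violation, and any device or app malfunction since the last survey (for the first survey, since installation). If the instruments already contain such items, say so in Sections 5.4 and 5.5. Describe the content of the end-of-intervention survey.

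Keep the spontaneous route in Section 8.1. State that the alerts in Sections 1.2 and 4.2 feed the adverse event log. List all reported events by arm and period, descriptively and without a formal comparison because counts will be too small. The dates matter because baseline precedes randomization and teens choose their own mode in follow-up.

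The cost is a few items in existing surveys and a minor amendment. The downsides are some recall error, remaining self-report bias, and higher reported counts than passive reporting would give.
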